1.3 Study Aims/Objectives

The primary objective of the CKD trial component is to determine the effectiveness of the FHT QI program for CKD compared to usual care for patients with a recorded diagnosis or pathology results consistent with a diagnosis of CKD receive guideline concordant care²⁻⁴ within 12-months post-randomisation to reduce CVD risk.

The secondary objectives of the trial are to determine the effectiveness of FHT QI program for CKD compared to usual care for patients with a recorded diagnosis or pathology results consistent with a diagnosis of CKD regarding the:

- a) proportion of patients that are prescribed an angiotensin-converting enzyme inhibitor (ACEI) or angiotensin receptor blockers (ARB) consistent with guidelines to reduce CVD risk²⁻⁴, prescribed during the 12-month follow-up period post-randomisation.
- b) proportion of patients who are prescribed statins consistent with guidelines to reduce CVD risk^{4,5}, prescribed during the 12-month follow-up period post-randomisation.
- c) mean systolic blood pressure (mmHg) using the most recent recorded reading at 12-months post-randomisation
- d) mean lipid results (total cholesterol, low-density lipoprotein (LDL) cholesterol, high-density lipoprotein (HDL) cholesterol and triglycerides all mmol/L) using the most recent recorded results at 12-months post-randomisation
- e) mean urine albumin:creatinine ratio (uACR) based on most recently recorded results at 12months post-randomisation
- f) proportion of patients with a reduction in uACR of at least 30% from baseline measurement
- g) proportion of patients classified as being at low, moderate, or high cardiovascular disease risk at 12-months post-randomisation
- h) mean eGFR (ml/min/1.73²) between baseline at 12-months post-randomisation
- i) rate of general practice encounters per patient over the 12 months post-randomisation.

For the health economics analysis, the aim is to quantify the costs of the delivery of the FHT QI program and the health care service costs. Specifically, the objectives are:

- j) to estimate the cost of the FHT software program installation for QI and cost of training for general practitioners to use the software
- k) to examine the primary health service utilisation and cost incurred by patients in the intervention arm compared to control arm over the 12-month period post-randomisation.

2. Trial Design

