(4) Change in mean lipid results (mmol/L) between baseline and the end of the trial. Patients' most recent lipid measurement at baseline, up to 12-months pre-trial (4th October 2020) will be compared to the most recently recorded measurement occurring within the trial period, at the end of the trial. The timing of lipid measurements may vary within and between study arms. Four types of lipids will be investigated:

- Total cholesterol
- LDL cholesterol
- HDL cholesterol
- Triglycerides

(5) Change in mean uACR between baseline and the end of the trial. Patients' most recent uACR measurement at baseline ($uACR_{baseline}$), up to 12 months before the trial start date (4th October 2020) will be compared to the most recently recorded measurement occurring within the trial period ($uACR_{12mth}$), at the end of the trial. The timing of uACR measurements may vary within and between study arms.

(6) The proportion of eligible patients whose uACR decreases by \geq 30%, defined as follows:

$$\frac{(uACR_{baseline} - uACR_{12mth})}{uACR_{baseline}} \ge 0.3$$

(7) The proportion of patients categorised as low (<10%), moderate (10 to 15%), and high risk (>15%) of CVD within the next 5-years based on the Framingham Risk Equation used by the Australian

management guidelines⁴. Patients will automatically be classified as being at high risk of CVD regardless of their Framingham 5-year risk if they have at least one of the following clinically conditions:

- Diabetes and age > 60 years
- Diabetes with microalbuminuria (> 20 mcg/min or uACR > 2.5 mg/mmol for males, > 3.5 mg/mmol for females)
- Moderate or severe chronic kidney disease (persistent proteinuria or eGFR< 45 mL/min/1.73 m2)
- A previous diagnosis of familial hypercholesterolaemia
- Systolic blood pressure \geq 180 mmHg or diastolic blood pressure \geq 110 mmHg
- Serum total cholesterol > 7.5 mmol

(8) The change in mean eGFR (ml/min/1.73²) between baseline and the end of the trial. Patients' most recent eGFR measurement at baseline, up to 12 months prior to the beginning of the trial (4th October 2021) will be compared to the most recently recorded eGFR measurement occurring within the trial period, at the end of the trial. The timing of eGFR measurements may vary within and between study arms.

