4.3 Other information extracted from the EMR that occur during the trial period

- Patient experienced ischemic stroke, heart attack, peripheral vascular disease, and/or kidney dialysis
- Pregnancy
- Patient deceased
- Time between most recent reported measurement at end of the trial in the EMR compared to baseline for secondary outcomes (1 to 8)

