4.6.2 Secondary outcomes

Statistical methods described for the primary outcome will be used for the **binary secondary outcomes 1, 2, and 6.** For each outcome, an additional covariate will be fitted in the regression model. For outcome 1, we will adjust for whether a recommendation would have been made to consider initiating ACEIs or ARBs for the patient (yes/no). Similarly for outcome 2, we will adjust for whether the recommendation would have been received to consider initiating statins (yes/no). For outcome 6, we will include uACR at baseline as a covariate.

For the analysis of continuous secondary **outcomes 3, 4, 5 and 8**, a mixed effects linear model with study arm, baseline measure of the outcome (where appropriate), randomisation stratification factors (GP FTE and IRSD terciles) will be fitted as fixed effects and general practice as a random effect. The estimated intervention effects will be reported as the difference in means between the intervention and active control arms with 95% confidence intervals and p-values.

Outcomes with a skewed distribution may be log-transformed, in which case, the estimated intervention effect will be reported as a ratio of the geometric means between study arms, with their respective 95% confidence interval and p-value.

Secondary outcome 7 will be analysed using the proportional odds logistic regression model with randomisation stratification factors (GP FTE and IRSD terciles) and baseline CVD risk group included as fixed effects. Generalised Estimating Equations with an exchangeable correlation structure and robust standard errors will be used to allow for correlation of outcomes within general practice. An alternative model will be considered if the assumption of proportional odds is not met.¹¹

The estimated intervention effect will be reported as a cumulative odds ratio with their respective 95% confidence interval and p-value.

Secondary outcome 9 will utilise a Poisson mixed effects model (or a Negative Binomial mixed effects model if overdispersion is detected), with fixed effects for study arm and the randomisation stratification factors (GP FTE and IRSD terciles), and random effect for general practice. The estimated intervention effect will be reported as differences in rate between the intervention and control arms and rate ratios with 95% confidence intervals and p-values.

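### CKD outcome 7 has no rule for established CVD or for CVD events during the trial, so a patient who has a heart attack can be scored as moved to a lower risk category

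*SAP*

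**What the plan says.** All references are to the CKD SAP.

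- **Objective.** Section 1.3(g) asks for the "proportion of patients classified as being at low, moderate, or high cardiovascular disease risk at 12-months post-randomisation".
- **Classification.** Section 4.1(7) defines the outcome as "The proportion of patients categorised as low (<10%), moderate (10 to 15%), and high risk (>15%) of CVD within the next 5-years", using the Framingham equation.
- **Override.** The same item adds that "Patients will automatically be classified as being at high risk of CVD regardless of their Framingham 5-year risk" when at least one of six conditions is present. Three of these are "Diabetes and age > 60 years", "A previous diagnosis of familial hypercholesterolaemia" and a kidney criterion, "Moderate or severe chronic kidney disease (persistent proteinuria or eGFR< 45 mL/min/1.73 m2". The other three are diabetes with microalbuminuria, very high systolic or diastolic pressure, and total cholesterol above 7.5.
- **Eligibility.** Section 2.1 excludes renal transplant or chronic dialysis, pregnancy, and patients who are inactive or deceased. It does not list prior CVD.
- **Events.** Section 4.3 extracts, for the trial period, "Patient experienced ischemic stroke, heart attack, peripheral vascular disease, and/or kidney dialysis". Section 4.5 summarises this information descriptively. The intercurrent-event analysis in section 4.7.1.2 covers death and pregnancy only.
- **Model.** Section 4.6.2 fits a proportional odds model by GEE, with the stratification factors and "baseline CVD risk group included as fixed effects".

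**The concern.** The program aims to lower CVD risk in people with CKD. A risk equation applied after a heart attack takes no account of that event unless the scoring rule says so. The rule here does not, although the events are in the data set. If lipids and blood pressure are lower after the event, the patient drops a category and the cumulative odds ratio takes this as benefit. A patient with CVD recorded before the trial can likewise be carried as low or moderate at both time points.

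A second feature affects how much the outcome can show. Every participant has CKD, and some automatic-high conditions will not go away in a year. Patients who have one of them stay high whatever happens to their blood pressure and lipids.

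**Working it through.** The SAP gives no sample size, effect size or category distribution for outcome 7, so there is no planned figure to reproduce. Two checks follow.

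**1. The rule applied to test patients.** The cut-points and overrides come from section 4.1(7). The Framingham scores are assumed.

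| Patient | Baseline | During trial | 12 months | Category change as written |
|---|---|---|---|---|
| A | score 12%, no override | heart attack | score 8%, no override | moderate to low |
| B | total cholesterol 7.6 (override) | heart attack | cholesterol 4.5, score 6% or 9% | high to low |
| B | as above | heart attack | cholesterol 4.5, score 12% or 14% | high to moderate |
| B | as above | heart attack | cholesterol 4.5, score 16% | high to high |

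If an in-trial event put the patient in the highest category, A would go from moderate to high and B would stay high. Neither would count as improved.

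The number affected is N × (share with recorded CVD or an in-trial event) × (share of those with no override and a score of 15% or less). The SAP gives none of these three terms.

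**2. Patients who cannot leave high.** The six conditions divide as follows.

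- Fixed over 12 months: diabetes with age over 60, and previously diagnosed familial hypercholesterolaemia.
- Unlikely to reverse: eGFR below 45.
- Able to change: diabetic microalbuminuria, proteinuria, blood pressure, total cholesterol.

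Let L be the share of patients fixed in high at both times. The SAP does not give it, so a range is used.

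- *Crude odds ratio for high.* Assume P(high) among movable patients is 0.50 in control and 0.40 in intervention. The whole-cohort probabilities are L + (1 − L) × 0.50 and L + (1 − L) × 0.40. At L = 0.4 they are 0.70 and 0.64, so the odds ratio is (0.64/0.36)/(0.70/0.30) = 0.76.
- *Odds ratio adjusted for baseline category, as planned.* This was simulated with a true log odds ratio of −0.5 (odds ratio 0.61) in movable patients. Their assumed baseline mix was 35/30/35% low/moderate/high, with n = 40,000, no clustering and one run per value of L.
- *Reference for z.* If fixed patients simply carry no information, z should shrink as 23.49 × √(1 − L).

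| L | Crude OR (true 0.67) | Adjusted OR (true 0.61) | Absolute z, adjusted | 23.49 × √(1 − L) |
|---|---|---|---|---|
| 0 | 0.67 | 0.61 | 23.5 | 23.5 |
| 0.2 | 0.72 | 0.64 | 19.4 | 21.0 |
| 0.4 | 0.76 | 0.62 | 18.5 | 18.2 |
| 0.6 | 0.79 | 0.67 | 12.9 | 14.9 |
| 0.8 | 0.82 | 0.63 | 10.4 | 10.5 |

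The crude ratio drifts steadily toward 1. The adjusted ratio shows at most a modest pull and no steady drift. Its standard error on the log scale runs from 0.5/23.49 = 0.021 to 0.465/10.42 = 0.045. The fall in z follows √(1 − L) closely, so the main loss is of information, and most of it would remain if the fixed patients were removed.

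**The case against.** Several arguments favour the plan.

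- A reader might infer that outcome 7 cannot answer objective (g). It can: (g) asks for this three-way classification at 12 months, and section 4.6.2 compares it between arms.
- A reader might infer that many patients are locked in high. The SAP gives no such share, and several of the overrides can reverse with treatment.
- A reader might infer that the odds ratio is badly diluted because the baseline covariate does not help. The large dilution belongs to a crude comparison that the SAP does not plan. Adjusting for baseline category removes most of it.
- A null result on outcome 7 would not leave the question of risk unexamined. Systolic pressure, four lipids, uACR and eGFR are analysed separately, and section 4.7.3 repeats the analyses by type 2 diabetes status.
- Restricting the main comparison to movable patients would leave the population named in the objective and the ITT approach of section 4.6, and would recover little precision.

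All of these stand, and they limit the second feature to reduced sensitivity.

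On CVD events, it can be said that they are reported by arm, that no frequency or between-arm imbalance is shown, that fuller eligibility criteria sit in a business requirements document that is not shown (section 2.4), and that forcing events into the top category makes a risk score partly a composite. These points bear on the size of the problem and on which rule to choose. They do not supply the missing rule. The scoring text is explicit, and it gives the result shown for patients A and B.

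**Conclusion.** The gap in scoring holds on the text alone. As written, a patient with known CVD can be classed low or moderate, and a patient with an in-trial event can be counted as moving to a better category. How often this happens, and which arm it would favour, cannot be told from the SAP. The finding is therefore a demonstrable misclassification of unknown frequency in one secondary outcome, not a shown bias of any given size. It rests on reading section 4.1(7) literally and on prior CVD not being excluded elsewhere.

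The lasting overrides are a lesser matter. They reduce the information that outcome 7 carries, by an amount that depends on a share not stated. All the figures for this part rest on assumed distributions and ignore clustering by practice.

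**What to change.** Before unmasking, in a revised SAP as section 4.8 allows:

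1. **Section 4.1(7) and section 4.6.2.** Analyse outcome 7 in patients without recorded CVD at baseline, or class recorded CVD as the highest category at both time points. Place any patient with an extracted stroke, heart attack or peripheral vascular disease event during the trial in the highest category at 12 months. Repeat the analysis under the rule as now written, as a sensitivity analysis.
2. **Baseline covariate.** Split high into high by a lasting override (diabetes with age over 60, familial hypercholesterolaemia, eGFR below 45) and high by score or by a reversible condition only. If nobody in the first group leaves high, that level predicts the outcome perfectly and the fit may fail, so name the unsplit covariate as the fallback.
3. **Reporting.** Give automatic-high counts at baseline by condition and arm. Add a supplementary analysis in patients with no lasting override, keeping the all-patient comparison as the main one.

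The in-trial events are already extracted. Recorded CVD at baseline is not in the section 4.2 list and would have to be added from the diagnosis records. Beyond that, the cost is a few lines of code and, if patients with prior CVD are left out, a slightly smaller denominator for one secondary outcome.

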2.4 Data Management and Workflow

General practice and practice staff characteristics will be collected via survey before randomisation.

Patient characteristics, baseline measures and outcome data will be measured using patient data extracted from general practice EMRs and stored in the Patron database. Patient data will be extracted from each practice using the GHRANITE tool at each data collection period namely, 4th October 2021 (baseline), 4th April 2022 (6 months), 4th July 2022 (9 months) and 30th September 2022 (12 months). The extracted data will be processed and curated by Patron data team members and stored within the Patron enclave using a separate database for each data collection period. This process takes at least two weeks.

The FHT QI module installed within practices as part of the FHT intervention interacts with the practice EMR system, running the FHT algorithms over patient data to identify patients with CKD or pathology consistent with CKD who could benefit from initiation of statins and/or ACEI/ARBs. The criteria used to identify the eligible patients with a recorded diagnosis or pathology results consistent with a diagnosis of CKD who attend general practice and the creation of the recommendations for guideline concordant care to consider (flags) are outlined in the Future Health Today business requirements document which was used to develop the FHT algorithms embedded in the technology platform. Within participating general practices individual patient level recommendations can be viewed. However, only aggregate level data is extracted by Future Health Today platform and available to the research team. As a result, these data are not linked with Patron database used for the trial statistical analysis.

Therefore, part of this curation process is the replication of the eligible patients and flags generated by FHT algorithms in the practices, patient outcomes and baseline measures, using identical algorithms to those embedded within, and executed by, FHT platform within the Patron dataset. These algorithms were independently validated by the biostatistician using baseline data. Limitation of this approach is that we will only be able to derive the action taken by clinicians if they were recorded in an extractable field in the EMR that is included in the Patron dataset, such as, medication prescriptions ordered, pathology results and observations.

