3.3 Adherence and protocol deviations

Protocol deviations include technical issues resulting in FHT being inaccessible for periods throughout the trial and preventing the extraction of data to the Patron system. Technical issues with FHT, practice computers/servers (preventing upload of data or function of FHT) or other technical issues that prevent staff from accessing FHT could negatively impact on the ability of GPs to participate in quality improvement program and to receive recommendations to facilitate delivery of guideline concordant care to patients within their cohort and may attenuate the effect of the intervention. Practices allocated to the active control arm will only have access the QI cancer-risk program.

4. Trial Population and Statistical Analysis

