(9) The rate of general practice encounters per patient over the trial period. This will be calculated using total number of general practice encounters in the 12-month trial period of all eligible patients with a diagnosis or pathology results consistent with CKD at baseline divided by the total time they were observed in the trial. For each patient, time will be one year, calculated from the date the trial commenced (4th October 2021) to the end of the trial (30th September 2022), except for patients/practices that discontinued during the trial period, where time observed will be calculated from the 4th October 2021 to the date the patient(s) discontinued/withdrew.

Health economics outcomes are:

(10) The cost of the installation for the software program for QI, training, QI support and education. This will be calculated at the general practice level, using cost data collected by Health and Biomedical Informatics Centre (HABIC R²) who developed and provided technical support for the FHT software and the FHT investigators and research team who liaised with practices and facilitated the education sessions.

(11) Cost of primary care service utilisation per patient per year. These will be calculated based on Medicare items, Provider Charge, Schedule Fee, Patient Out of Pocket in the Medicare Benefits Schedule (MBS) data linked to patients in the Patron for the FHT evaluation.

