4.4 Withdrawal and Follow-up

Staff within practices and/or the practice may withdraw at any time. If a practice withdraws then no further patient data will be extracted from the EMR system. However, existing data (prior to notice of withdrawal) will be used in the final analysis unless the practice requests existing data also be excluded. Individual patients can also withdraw their data by notifying their general practice that they no longer consent to their data being used for research purposes. As the intervention is applied at the general practice level within the EMR system this means that no further patient data will be extracted. However, existing data (prior to notice of withdrawal) will be used in the final analysis unless the participant requests existing data also be excluded.

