4.5 Descriptive analysis

The flow of practices and eligible patients from recruitment to trial end, will be shown in a CONSORT diagram¹, see Appendix Figure 1 for the template. The report will include the number of practices approached for involvement in the trial, the number of practices that met study eligibility criteria, the number practices consented and randomised by their allocated study arm, together with the total number and the mean number of eligible patients per practice and number that were included in the intention to treat analysis. The number of practices and/or patients who withdraw or discontinue will also be summarised by study arm and period that the withdrawal/discontinuation occurred (0-6 months, 7-9 months, 10-12 months). When such information is available, the reason a practice/patient withdrew or discontinued the intervention will be reported by study arm.

Descriptive statistics will be used to describe general practice and patients' baseline characteristics and baseline outcome measures overall and by study arm as outlined in Appendix B Table 1 and Table 2. Descriptive statistics will also be used to summarise other information extracted from the EMR that occur during the trial period by study arm and overall. Categorical data will be summarised using counts and percentages, according to the number of eligible patients with available data. Continuous data will be summarised using arithmetic mean, standard deviation if the data have a symmetric distribution. When appropriate, continuous outcome data with a right skewed distribution may be presented as a geometric mean instead of an arithmetic mean. Otherwise, if the distribution if the data is non-symmetrical, the median and interquartile range (25th and 75 percentiles) will be presented instead. The intra-cluster correlation coefficient with 95% intervals will also be reported for baseline patient measurements estimated using one-way analysis of variance.

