- (4) Proportion of eligible patients whose sex at birth is coded as male in the EMR in the closed and open cohort with one raised PSA that have been followed up according to Cancer Council Australia guidelines⁴ within the 12-month trial period. Relevant investigations include a repeat PSA test, free to total PSA percentage and/or referral to a urologist^{5,8}. The absence of any of relevant recorded investigation during the trial period will be considered equivalent to not being investigated.
- (5) Proportion of eligible patients in the closed and open cohorts that have a new recorded diagnosis of prostate, oesophageal, gastric, colorectal, endometrial, lung or ovarian cancer recorded in the general practice EMR within the 12-month trial period. The absence of any of recorded diagnosis during the trial period will be considered equivalent of no diagnosis being made.
- (6) The rate of general practice encounters per eligible patient over the 12-month trial period. This will be calculated using total number of general practice visits over the trial period of all eligible patients identified as at risk of an undiagnosed cancer in the closed cohort divided by the total time they were observed in the trial. For each patient, time will be calculated from the date the trial commenced (4th Oct 2021) to the end of the trial (30th September 2022). If the patient enters in the open cohort, the time observed will be calculated from the date they the trial to the end of the trial (30th September 2022). For patients/practices that discontinue during the trial period, time observed will be calculated from they entered the (namely, the 4th October 2021 for the closed cohort or date they first report of an abnormal test result for the open cohort) to the date the patient(s) discontinued/withdrew from the trial.

(7) Time to investigation for patients with abnormal pathology results identified as at risk of an undiagnosed cancer in the open cohort. This includes any investigation, treatment, review of symptoms or referrals as described in the primary outcome. Time to investigation will be defined as the number of days between the initial altered test result date and the first investigation (retesting, investigations, treatments, referrals and review of symptoms). Outcomes will be assessed at 12 months from baseline and patient records without follow-up action by this time will be censored.

Health economics outcomes are:

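### Encounter rate outcomes count observed time up to withdrawal, although encounters are captured only up to the last data extraction

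*SAP*

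**What the plan says.** CKD SAP section 4.1 defines outcome 9 as a ratio. The numerator is the "total number of general practice encounters in the 12-month trial period of all eligible patients". The denominator is total observed time. Each patient is given one year, from 4 October 2021 to 30 September 2022. Those who leave early are the exception, and for them the rule reads: "where time observed will be calculated from the 4th October 2021 to the date the patient(s) discontinued/withdrew". Section 4.6.2 names a Poisson or negative binomial mixed model but does not define exposure again, so section 4.1 is the only definition.

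CKD SAP section 2.4 lists the extraction dates: "namely, 4th October 2021 (baseline), 4th April 2022 (6 months), 4th July 2022 (9 months) and 30th September 2022 (12 months". Section 4.4 states: "If a practice withdraws then no further patient data will be extracted from the EMR system". The same holds for individual patients who withdraw. Data that already exist are kept unless their removal is requested, and no closing extraction at withdrawal is provided for.

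Section 3.3 lists among the protocol deviations "technical issues resulting in FHT being inaccessible for periods throughout the trial and preventing the extraction of data to the Patron system".

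The cancer-risk SAP has the same extraction dates (section 2.5) and the same withdrawal rule (section 4.4.1). Its outcome 6 (section 4.2) also runs time "to the date the patient(s) discontinued/withdrew from the trial".

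**The concern.** A rate needs its events and its time at risk to cover the same interval. Here the time for a practice or patient that withdraws runs to the withdrawal date, while the events stop at the last extraction before it. The gap can be as long as 181 days.

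The error always lowers the rate of those who withdraw. Practices withdraw as whole clusters, so balance between arms cannot be taken for granted. If withdrawal is more common in one arm, or falls at less favourable times, the error passes into the rate difference and the rate ratio. The CKD SAP's missing-data section (4.7.1.3) covers the primary outcome and outcomes 3 to 8, so nothing there would pick the problem up for outcome 9.

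**Working it through.** The SAPs state no expected rate, sample size or power for these outcomes, so there is no planned figure to reproduce. The check is date arithmetic on the SAPs' own dates, for patients whose time starts on 4 October 2021, with a constant encounter rate and no deaths.

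**1. Extraction days, counted from 4 October 2021.** 4 April 2022 is day 182, 4 July 2022 is day 273 and 30 September 2022 is day 361.

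**2. Rate for a single withdrawal.** Rate under the plan ÷ true rate = (last extraction day on or before withdrawal) ÷ (withdrawal day).

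| Withdrawal day | Last extraction day | Ratio |
|---|---|---|
| 90 | 0 | 0.00 |
| 181 (3 April 2022) | 0 | 0.00 |
| 227 | 182 | 0.80 |
| 272 (3 July 2022) | 182 | 0.67 |
| 316 | 273 | 0.86 |
| 360 | 273 | 0.76 |

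The ratio is 1.00 only when withdrawal falls on an extraction date.

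**3. Withdrawals spread evenly over days 1 to 360.** For 181 of those days the last extraction is day 0, for 91 it is day 182, and for 88 it is day 273.

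- Mean days with data: (91 × 182 + 88 × 273) ÷ 360 = 40,586 ÷ 360 = 112.7.
- Mean days counted: 180.5.
- Ratio: 112.7 ÷ 180.5 = 0.62.

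**4. Effect on one arm.** The share withdrawing, s, is not in the documents and is assumed. Arm rate ÷ true rate = [(1 − s) × 361 + s × days with data] ÷ [(1 − s) × 361 + s × days counted].

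For s = 10%:

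- Evenly spread: (324.9 + 11.27) ÷ (324.9 + 18.05) = 336.17 ÷ 342.95 = 0.980.
- Worst case, all on day 181: 324.9 ÷ (324.9 + 18.1) = 324.9 ÷ 343.0 = 0.947.

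| s | Evenly spread | All on day 181 |
|---|---|---|
| 2% | 0.996 | 0.990 |
| 5% | 0.990 | 0.974 |
| 10% | 0.980 | 0.947 |
| 20% | 0.958 | 0.889 |

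**5. From arm rate to rate ratio.** If only one arm loses patients, the factor above is the expected rate ratio when the truth is 1.00. If one arm loses 10% and the other 5%, both evenly spread, it is 0.980 ÷ 0.990 = 0.99. If share and timing are equal, it is 1.00.

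**6. Final extraction that fails and is never recovered.** A practice that has not withdrawn is credited with the whole trial period but has data to day 273 at most: 273 ÷ 361 = 0.76, which is 24% too low. If this affects 10% of one arm: (324.9 + 27.3) ÷ 361 = 0.976.

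**7. After the correction.** Days with data equal days counted, so the ratio is 1.00 for every withdrawal day. A withdrawal before 4 April 2022 then contributes no encounters over no time, where the plan has no encounters over up to 181 days.

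**The case against.** The best defence is that the effect is small and may cancel. The outcome is secondary, the cancer-risk SAP (section 4.5.5) expects few individual patients to withdraw their data, and equal loss at equal times leaves the rate ratio unbiased. The larger figures need loss in one arm only, timed just before an extraction. They are also pooled arm-level ratios, not the bias of the planned mixed model. All of this stands and limits the size. It does not make the denominator right.

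A reader might go further and infer the reverse error. CKD SAP section 4.5 speaks of why "the reason a practice/patient withdrew or discontinued the intervention will be reported by study arm". If *discontinued* in outcome 9 meant stopping use of FHT, a practice still being extracted would have its time cut while its encounters ran on, contrary to the intention-to-treat rule in section 4.6. The documents do not support that reading as the plan's rule. Outcome 9 joins the two words as one event, and the cancer-risk SAP ties both to leaving the trial. The word is undefined and should be clarified, but no inflated rate can be charged to the plan.

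A reader might also infer that any failed extraction loses encounters. An extraction missed at 6 or 9 months need not, if a later one recovers the history. Only an unrecovered final failure matters, and the SAP describes none.

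Lastly, calling 361 days one year is a discrepancy of about 1% (361 ÷ 365 = 0.989), common to completers in both arms, so it nearly cancels.

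**Conclusion.** The mismatch is real and follows from the SAPs' own rules on extraction, withdrawal and observed time. It affects CKD outcome 9 and cancer-risk outcome 6. The primary outcomes are untouched.

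The rate for those who withdraw is too low: zero before the 4 April 2022 extraction, and about 0.62 of the true rate on average if withdrawals are evenly spread. Bias in the rate ratio requires the share or timing of withdrawal to differ between arms. At an assumed 10% in one arm only, it is about 0.98 with even spread and 0.947 at worst. With equal share and timing the rate ratio is unbiased, but both arm rates, and therefore the rate difference, are still scaled down by the same factor.

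These figures rest on a constant encounter rate, no deaths, an assumed share withdrawing and pooled arm-level rates. The point deserves correction because the rule is wrong as written and the remedy is cheap, not because a large bias has been shown.

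**What to change.** In CKD SAP section 4.1 (outcome 9) and cancer-risk SAP section 4.2 (outcome 6):

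- End each patient's time at the earliest of the last successful extraction containing that patient's data, recorded death, and 30 September 2022. Death has to be named: deaths are recorded and patients who die stay in the analysis, so running time to the extraction date alone would count time after death.
- Count only encounters dated within that same interval.
- Use actual days as the exposure, 361 for completers.
- Report patients with no post-baseline extraction as missing for this outcome.
- State that *discontinued* means leaving data extraction, so that stopping FHT alone does not shorten observed time under intention to treat.

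The cost is a change of wording in two definitions. The extraction dates belong to the existing data workflow, and no new data are needed. The downside is that practices with no post-baseline extraction no longer contribute to this secondary outcome. Under the present rule they contribute a false zero.
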